4.5 Efficacy Variables

The primary efficacy variable will be the change from baseline to the Week 52 assessment in the PSP Rating Scale (PSPRS) total score to assess the effect of ABBV-8E12 in slowing disease progression.

Secondary efficacy variables include the changes from baseline of Unified Parkinson's Disease Rating Scale (UPDRS) Part II score, Clinical Global Impression of Severity and

Change (CGI-S, CGI-C) score, the Schwab and England Activities of Daily Living Scale (SEADL) score, PSP-Quality of Life (PSP-QoL) total score, PSP Staging System and time to loss of ability to walk independently as measured by PSPRS item 26, PSPRS domain scores, and regional (midbrain, frontal lobes, and third ventricle) and whole brain atrophy as measured by volumetric MRI.

Exploratory efficacy variables include the Natural History and Neuroprotection in Parkinson Plus Syndromes-Parkinson Plus Scale (NNIPPS-PPS) total score and dimensional scores, Patient Global Impression of Change (PGI-C) score, Letter Fluency Test (LFT) score, Repeatable Battery for Assessment of Neuropsychological Status (RBANS) total scale score and subtest scores, Color Trails Test (CTT) (Parts 1 and 2) completion time, EuroQoL-5D (EQ-5D) summary index score. Exploratory quantitative MRI measures may additionally be evaluated; including diffusion tensor imaging (DTI) derived fractional anisotropy (FA) and diffusivity measures [radial diffusivity (RD), mean diffusivity (MD), and axial diffusivity (AD)] to assess changes in microstructural integrity.

4.6 Safety Variables

The following safety variables will be analyzed for the study: adverse event (including infusion and allergic reactions), vital signs, C-SSRS, laboratory tests, ECG, and MRI safety evaluations.

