This study will utilize a DMC consisting of at least 2 external clinicians, at least 1 external statistician, and at least 1 external pharmacokineticist. The DMC will review unblinded safety and efficacy data and make recommendations to the Sponsor based on the totality of available clinical data. The DMC memberships, responsibilities and operating logistics will be documented in a charter that will be prepared prior to the first DMC review meeting.

In addition to blinded safety data monitoring by the Sponsor, the first three mandatory DMC reviews of unblinded safety data will take place after the 10th, 20th, and 30th subjects in Cohort 1 have received their second dose and results for the Day 15 Safety labs and the MRI performed within 2 weeks after their second dose are available. The dataset reviewed will include all of the available safety and pharmacokinetic data in the study, including the data of any subjects from Cohort 2 who have received at least one dose of study drug.

For Cohort J1, an additional mandatory DMC review will take place after the 9th subject enrolled in Japan has received their second dose and results for the Day 15 Safety labs and the MRI performed within 2 weeks after their second dose, are available. Only after the DMC has recommended to continue enrollment into the study without modification, will Japanese subjects be enrolled into Cohort 2.

Additional DMC reviews of available safety data will occur after a total of approximately 80, 130, 180, 240, and 330 subjects are randomized and every 6 months thereafter until the study has completed. Ad hoc meetings may occur as needed.

Doses may be decreased after the evaluation by the DMC of available safety, tolerability and PK data.

Long-Term Extension Study:

If ABBV-8E12 is safe and well tolerated in the current study, a long-term extension study will be developed and implemented under a separate protocol.

Post-Treatment Follow-Up:

All subjects who would not enter the separate long-term extension study for extended treatment (including subjects who prematurely discontinue from treatment, or would decline to participate in or would not qualify for the long-term extension study) will enter the Post-treatment Follow-up Period within this study.

A schematic of the study design is shown in [Figure 1](#). A table of sample size and dosing groups is provided in [Table 3](#).

Figure 1. Study Schematic

[figure not shown]

Table 3. Sample Size

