6.1.7 Toxicity Management

For the purpose of medical management, all adverse events and laboratory abnormalities that occur during the study must be evaluated by the investigator.

A drug-related toxicity is an adverse event or laboratory value outside of the reference range that is judged by the investigator or AbbVie as a "reasonable possibility" of being related to the study drug (Section 6.1.3). Toxicity is deemed "clinically significant" based on the medical judgment of the investigator. The following guidelines should be used for study drug-related toxicity management.

Potential Drug-Related Toxicities

No potential drug related toxicities were identified from preclinical or clinical studies conducted to date. Examples of safety concerns that could be hypothetically associated

with ABBV-8E12 and safety concerns associated with monoclonal antibodies, in general, are summarized below.

On-Target Toxicities

The brain appears to be the only organ to express tau at significant levels. Tau is an intracellular protein mainly expressed in neurons, although lower levels can be found in astrocytes and oligodendrocytes. ABBV-8E12 is directed against extracellular tau and no function of extracellular tau has been reported. No cellular uptake of the mouse version of ABBV-8E12 antibody bound to tau aggregates was detected in preclinical studies.²⁸ The likelihood of adverse on-target side effects of an anti tau immunotherapy is therefore anticipated to be low.

Non-Specific Off-Target Toxicities

Potential toxicities resulting from the non-human origin of ABBV-8E12 include allergic reactions or infusion reactions, including anaphylaxis or anaphylactoid reactions, flu-like symptoms, including fever, fatigue or loss of appetite, or rash. ABBV-8E12 is lacking the Fragment Crystallizable (Fc) effector function activity and therefore Fc-mediated antibody-dependent cellular cytotoxicity and complement-dependent cytotoxicity is not expected. In addition, ABBV-8E12 exhibited a favorable in vitro immune-safety profile. No infusion reactions have occurred in the single dose PSP clinical study or in the Expanded Access protocol (Studies C₂N-8E12-EA-001 and C₂N-8E12-DE-003).

Allergic Reactions Management

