Subjects will be closely monitored for treatment-related adverse events, including allergic reactions, during the infusion. For their first 4 ABBV-8E12 infusions, subjects should be monitored on site until 2 hours post-infusion. For subsequent infusions, subjects should be monitored on site until at least 30 minutes after the end of infusion. Subjects in Cohort J1 will be confined for a minimum of 24 hours following their first infusion. The Investigator will assess safety 2 days after the first infusion, either while in hospital or as an outpatient. From their second to fourth infusion, Cohort J1 subjects will be observed

on-site for at least 2 hours following each infusion of study drug. Subjects in Cohort 2 will be observed on-site for at least 2 hours following each of the first 4 infusions of study drug. Following the 4th infusion, all subjects should be monitored on-site for at least 30 minutes after the end of infusion. Longer observation periods and more frequent vital sign checks may be required in subjects who experience infusion reactions. In general, Infusion reactions are more frequently observed during the first infusion and within 24 hours from the start of administration, especially within the first 2 hours.²⁹ Please refer to [Table 2](#), Safety Observation Period Following Infusions, for a summary of the observation periods following infusions.

Severe or life-threatening allergic reactions require the immediate interruption of ABBV-8E12 treatment and permanent discontinuation from further treatment. Appropriate medical therapy including epinephrine, corticosteroids, intravenous antihistamines, bronchodilators, and oxygen should be available for use in the treatment of such reactions. Subjects should be carefully observed until the complete resolution of all signs and symptoms.

Moderate infusion reactions resolving with supportive care should be discussed with the TA MD, and a reduction of the infusion rate for future administrations can be considered.

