8.1.6 Safety Analyses

All safety analyses will be performed on the safety data set unless otherwise specified. Comparisons between each ABBV-8E12 dose group and placebo will be performed with two-sided test at the significance level of 0.050, if applicable. All safety assessments that are taken no more than 20 weeks after the last dose of study drug administration will be included in the safety evaluation of the Double-blind Treatment Period, and all safety assessments that are taken more than 20 weeks after the last dose of study drug will be included in the safety evaluation for the Post-treatment Follow-up Period.

Study Drug Exposure and Compliance

The number of doses on study drug will be summarized by treatment group and all treatment groups combined. The number and percentage of subjects with at least 90% compliance with study drug dosing will be summarized by treatment group and all treatment groups combined.

Adverse Events

A treatment-emergent adverse event (TEAE) is defined as any adverse event that begins or worsens in severity on or after the first study drug dose date and no more than 20 weeks after the last study drug dose date.

All other safety assessments that are taken no more than 20 weeks after the last dose of study drug will be included in the safety evaluation of the Double-blind Treatment Period, and all safety assessments that are taken more than 20 weeks after the last dose of study drug will be included in the safety evaluation for the Post-treatment Follow-up Period.

Unless otherwise specified, treatment group differences in continuous safety variables (e.g., change from baseline to final observation on laboratory tests) will be assessed using an ANOVA model with treatment as the main effect, and the treatment group differences in binary safety variables will be evaluated using Fisher's exact test.

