11.2 Analysis of Adverse Events

All adverse events will be coded using the most current version of the Medical Dictionary for Regulatory Activities (MedDRA). A treatment-emergent adverse event (TEAE) is defined as any adverse event that begins or worsens in severity on or after the first study drug dose date and no more than 20 weeks after the last study drug dose date. Analysis of adverse events will also be conducted by geographical region (North America including US and Canada, European countries plus Australia, and Japan).

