11.2.2 Adverse Event Incidence

TEAE incidence will be summarized and presented using primary MedDRA system organ classes (SOCs) and preferred terms (PTs). The system organ classes will be presented in alphabetical order and the preferred terms will be presented in alphabetical order within each system organ class. Subjects reporting more than one adverse event for a given MedDRA PT will be counted only once for that term. Subjects reporting more than one adverse event within a SOC will be counted only once for the SOC total. Subjects reporting more than one adverse event will be counted only once in the overall adverse event total.

The number and percentage of subjects experiencing one or more TEAEs will be summarized by PT for each treatment group, ABBV-8E12 Overall. The PTs will be presented by decreasing frequency in ABBV-8E12 Overall.

The number and percentage of subjects experiencing one or more adverse events in the following adverse event categories will be summarized by primary SOC and PT for each treatment group, ABBV-8E12 Overall.

- Any TEAE
- Any serious TEAE
- Any TEAE that led to discontinuation of study drug

- Any TEAE assessed by the investigator to have Reasonable Possibility of Being Related to study drug

The number of subjects experiencing one or more TEAEs will also be summarized by maximum severity category (mild, moderate, severe and unknown) and primary SOC and PT for each treatment group, ABBV-8E12 Overall. Subjects reporting more than one TEAE for a given PT will be counted only once for that term in the most severe category reported. If a subject has an adverse event with unknown severity, then the subject will be counted in the severity category of "unknown" even if the subject has another occurrence of the same event with a severity present. The only exception is if the subject has another occurrence of the same adverse event with the most extreme severity – "Severe." In this case, the subject will be counted under the "Severe" category. No comparisons of treatment groups will be performed.

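### SAP 11.2 has no table pooling infusion- and allergic-reaction terms, so a reaction recorded as several generic symptoms is split across single preferred-term rows (minor)

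*SAP*

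**What the plan says.** SAP 4.6 gives the safety variables to be analysed as "adverse event (including infusion and allergic reactions), vital signs, C-SSRS, laboratory tests, ECG, and MRI safety evaluations".

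SAP 11.2 to 11.2.3 then plan an overview, incidence by preferred term (PT) and by system organ class (SOC) and PT, maximum severity, maximum relationship, a regional breakdown and listings. A treatment-emergent event may start up to "no more than 20 weeks after the last study drug dose date". One SOC/PT table is restricted to "Any TEAE assessed by the investigator to have Reasonable Possibility of Being Related to study drug". Protocol 8.1.6.1 also tabulates by SOC and PT, and Protocol 8.1.6 supplies a default test: "the treatment group differences in binary safety variables will be evaluated using Fisher's exact test".

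Protocol 6.1.7 names allergic and infusion reactions as potential toxicities, together with "flu-like symptoms, including fever, fatigue or loss of appetite, or rash". It says infusion reactions are more frequent at the first infusion and "within 24 hours from the start of administration, especially within the first 2 hours". Protocol 6.1 has the investigator record an onset date and a diagnosis if one is known, otherwise a sign or symptom. Protocol 5.5.1 has infusion start and stop times recorded to the minute.

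The post-treatment follow-up in Protocol 5.1 covers "All subjects who would not enter the separate long-term extension study for extended treatment", so extension entrants have a shorter window.

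**The concern.** The protocol describes these reactions by two features: a set of symptoms, and closeness to an infusion. No table in SAP 11.2 uses either feature. By contrast MRI safety, another item in the SAP 4.6 list, has its own output in SAP 11.6.3.

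A patient who has fever after one infusion and rash after another, each entered as a symptom, adds one to the fever row and one to the rash row. Both rows also hold unrelated events from the whole window. An SOC total pools terms by organ class, not by reaction. Only the any-event and related-event lines of the overview (SAP 11.2.1) bring such terms together, and they do so with every other kind of event. The related-event line also depends on each investigator's causality call.

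Long-term safety and tolerability is a primary objective, and the product is a monoclonal antibody infused 14 times. At stake is a readable by-arm comparison of mild and moderate reactions, which the serious-event and discontinuation tables would largely miss.

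**Working it through.** **Length of the count.** Doses fall on Days 1, 15 and 29, then every 28 days to dose 14: 29 + 11 × 28 = Day 337 (Week 48). Adding 140 days gives Day 477, and 477/7 = 68.1 weeks. This agrees with the last follow-up visit at Week 68. Early discontinuers and extension entrants have less.

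**Inputs.** From the documents: 110 per arm (SAP 4.3) and two-sided 0.05 (SAP 11.1), with Fisher's exact test as the protocol's default. All the following are assumptions, because the documents give no rates:

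- added reaction risk *e* = 8%;
- background *b* per generic PT over the full window = 5%, 10% or 20%;
- 20% of background events judged related;
- an infusion window of the infusion day plus the next day, a fraction *f* = 14 × 2/477 = 0.0587 of the time, or 3 × 0.0587 = 0.176 if background onsets cluster threefold on those days;
- capture of true reactions of 100% or 80% (*e* = 0.08 or 0.064).

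**Formulas.** The placebo proportion p0 is *b* for a full-window PT row, 0.2*b* for a related-event PT row, 1 − (1 − *b*)^*f* for one PT in the window, and 1 − (1 − *b*)^(4*f*) for four pooled PTs in the window. The active proportion is p1 = 1 − (1 − p0)(1 − *e*). Power is the exact binomial probability of Fisher p ≤ 0.05.

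**Infusion-specific diagnosis, no background.** For 8% versus 0%, power is 88%. Nothing material is lost.

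**Whole excess in one generic PT** (power at *b* = 5/10/20%):

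| Table | 100% capture | 80% capture |
|---|---|---|
| Full-window PT row (counts every reaction) | 43/28/16% | – |
| Related-event PT row | 73/63/49% | 55/46/34% |
| Infusion window, threefold clustering | 75/65/49% | 57/47/35% |

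With equal capture and clustering, the window and the planned related-event table are level. Only without clustering is the window ahead (83/78/70% at full capture).

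**Excess spread over four generic PTs**, 8%/4 = 2% each:

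| Table | Power at *b* = 5/10/20% |
|---|---|
| Any one full-window PT row | 5/5/4% |
| Any one related-event PT row | 4/5/5% |
| Pooled list, infusion window, full capture | 71/60/43% |
| Same, threefold clustering | 51/35/21% |
| Same, clustering and 80% capture | 36/24/15% |

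For example, at *b* = 10% without clustering, p0 = 1 − 0.9^0.2348 = 0.0244 and p1 = 1 − 0.9756 × 0.92 = 0.1025, giving power 0.595. The 95% CI half-width is 1.96 × √[(0.0244 × 0.9756 + 0.1025 × 0.8975)/110] = 6.4 points.

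A reader who scans all four full-window rows has at most the sum of their powers, about 4 × 5.3% = 21% at 5% background and 4 × 4.2% = 17% at 20%.

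**Pooled list without the window.** At *b* = 10%, p0 = 1 − 0.9^4 = 0.344 and p1 = 0.396, giving 10% power (17% and 6% at *b* = 5% and 20%). That row is descriptive.

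**Any event in the window.** With 2, 4 or 6 background onsets per subject, p0 = 1 − exp(−2*f*) and so on. Power is 26/16/12%, or about 12/7/5% with threefold clustering. Such a table would show little.

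**The case against.** The strongest reply is that nothing promised is missing. SAP 4.6 names the reactions in a parenthesis, as a kind of adverse event, and SAP 11.2 does analyse adverse events. A reader might infer that the SAP commits to a separate reaction table and then omits it. The documents do not support that, since neither promises one.

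The protocol also favours recording a diagnosis. It asks for one where known, has sites watch for infusion reactions, requires at least 2 hours of observation after each of the first four infusions, and sends moderate infusion reactions to the medical director. Reactions identified in this way are well shown by the planned tables. Nothing in the documents says how often the generic-symptom route would occur.

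A reader might also infer a large power gain from adding an infusion window to any single PT. That holds only if background onsets do not cluster on infusion days, which are also visits at which adverse events are assessed, or if the window is credited with full capture and the related-event table is not. On equal terms there is no gain.

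Other cover exists: the serious-event and discontinuation tables, and repeated unblinded safety reviews by the data monitoring committee. The charter is not available here, so what those reviews show is unknown, and they are not a final by-arm output. Protocol 6.1.7 reports no infusion reactions in the earlier studies, but few patients were treated. The safety tests carry no decision rule.

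All of this stands, and it limits the point to reactions split over several generic terms. For those, the reply offers only the related-event overview line, which mixes in every other related event.

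**Conclusion.** The gap is real but minor. Reactions recorded as an infusion-specific diagnosis, or carried by one generic term, are adequately served by the planned tables. A syndrome spread over several generic terms is not: each single row has about 4–5% power under the assumed four-way split, against 71/60/43% for a pooled list in the infusion window, 51/35/21% with clustering, and 36/24/15% with clustering and 80% capture. At the least favourable corner (20% background, clustering, 80% capture), the 15% is no better than the 17% upper bound from scanning four rows, so the advantage is not guaranteed.

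These figures rest on assumed rates, an even four-way split and independent onsets. They show direction and rough size only. Onset is recorded as a date, so a day-level window will admit some events that began before the infusion. Infusion reactions are described only as more frequent within 24 hours, and no timing is given for allergic reactions, so some will fall outside the window.

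**What to change.** Add one by-arm table to SAP 11.2: subjects with at least one treatment-emergent event from a hypersensitivity/infusion-reaction term list fixed before unblinding, with onset on an infusion day or the next day. Show the same list without the window in a second block, to catch delayed allergic reactions. Give the risk difference and 95% CI for each dose versus placebo. State in a footnote that onset is by date and may include pre-infusion events. Keep the planned SOC/PT and related-event tables. A windowed table of any event is not worth adding.

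The cost is one table and a term list to agree. No new data are needed, since onset dates and infusion times are already collected. If the list is not fixed before unblinding, any later grouping will be post hoc.

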4.7 Pharmacokinetic Variables

Values for the following pharmacokinetic parameters will be determined using non-compartmental methods: maximum observed serum concentration (C_{max}), the time to C_{max} (peak time, T_{max}), the area under the concentration time curve (AUC) over the dosing interval after the first and the fifth doses in Cohort 1 and Cohort J1; and the observed serum concentration at the end of a dose interval (C_{trough}) in all subjects.

4.8 Biomarker and Pharmacogenetic Research Variables

4.8.1 Biomarker Research Variables

Blood and CSF samples will be collected to conduct research to investigate disease-related and drug-related biomarkers. The biomarkers to be analyzed may include, but are not limited to, the following:

- CSF and serum/plasma samples will be assayed for free/total tau to demonstrate tau binding of ABBV-8E12.
- CSF or serum/plasma samples may be analyzed for biochemical or macromolecular factors (e.g., NFL) related to the pharmacodynamics and safety of ABBV-8E12.

Exploratory evaluations from samples may include analyzing biomarkers related to the pathway(s) targeted by the study drug or believed to be related to the disease or to drug response. Analysis of these exploratory biomarkers will be described in a separate biomarker document.

The information learned from analyzing these data may be used to investigate factors impacting response to treatment, scientific questions related to PSP, support development of ABBV-8E12, or in the development of new therapies. Furthermore, given the exploratory nature of these data the results may not be included in the clinical study report (CSR).

4.8.2 Pharmacogenetic Research Variables

MAPT haplotype status may be determined for each subject and analyzed as a factor contributing to the subject's response to study treatment. The MAPT haplotype results may be analyzed as part of a multi-study assessment of MAPT and response to ABBV-8E12 treatment. The results may also be used for the development of diagnostic tests related to ABBV-8E12, or other drugs in development for PSP or related conditions. The MAPT haplotype results may not be included in the CSR.

Optional pharmacogenetic samples may be collected to conduct exploratory investigations into known and novel biomarkers. The types of biomarkers to be analyzed may include, but are not limited to, nucleic acids, proteins, lipids or metabolites. The samples may be analyzed as part of a multi-study assessment of factors influencing the subjects' response to the study drug (or drugs of the same or similar class) or the development and progression of the subjects' disease or related conditions. The samples may also be used to develop new diagnostic tests, therapies, research methods or technologies. The results from these analyses are exploratory in nature and may not be included in the CSR.

